6.1.1 Study Setting

The study will be conducted primarily in secondary and tertiary care hospitals within the United Kingdom.

6.1.2 Site/Investigator Eligibility Criteria

Once a site has been assessed as being suitable to participate in the trial, the trial team will provide them with a copy of this protocol and the Summary of Product Characteristics (SPC).

To participate in the PUFFIN trial, investigators and trial sites must fulfil a set of criteria, agreed by the PUFFIN Trial Management Group (TMG), as defined below. In exceptional circumstances, a site may be excluded from some aspects of the study if they do not meet the criteria below following approval from the CI.

Eligibility criteria:

- A named clinician is willing and appropriate to take Principal Investigator (PI) responsibility.
- Suitably trained staff are available to recruit participants, undertake/observe study assessments and measurements, enter data and collect and store samples.
- The site has a suitable potential patient population to adequately recruit participants from.

Sites are required to have access to a pharmacy able to store, prepare and dispense Investigational Medicinal Product (IMP).

In addition, selected sites will be invited to participate in the PUFFIN sputum sub-study and will approach and consent eligible patients accordingly.

Trial sites meeting eligibility criteria will be issued with a PUFFIN Investigator Site File (ISF) and a pack of documentation needed by the Research and Development (R&D) Department of their Trust to enable the Trust to provide confirmation of capacity and capability to undertake the study.

6.1.2.1 Principal Investigator's (PI) Qualifications and Agreements

The investigator(s) must be willing to sign an investigator statement to comply with the trial protocol (confirming their specific role and responsibilities relating to the trial, and that their site is willing and able to comply with the requirements of the trial (see section 12)). This includes confirmation of appropriate qualifications, familiarity with the appropriate use of any investigational products, agreement to comply with the principles of GCP, to permit monitoring and audit as necessary at the site, and to maintain documented evidence of all staff at the site who have been delegated significant trial related duties.

6.1.2.2 Resourcing at site

The investigator(s) should be able to demonstrate a potential for recruiting the required number of suitable subjects within the agreed recruitment period (i.e. the investigator(s) regularly treat(s) the target population). They should also have an adequate number of qualified staff and facilities available for the foreseen duration of the trial to enable them to conduct the trial properly and safely.

Sites will be expected to complete a delegation of responsibilities log and provide staff contact details. GCP training is required for all staff responsible for trial activities. The frequency of repeat training may be dictated by the requirements of their employing institution or 2 yearly where the institution has no policy, and more frequently when there have been updates to the legal or regulatory requirements for the conduct of clinical trials.

The site should have sufficient data management resources to allow prompt data return to NCTU.

6.2 Site approval and activation

The Clinical Trial Authorisation (CTA) for the trial requires that the Medicines and Healthcare products Regulatory Agency (MHRA) is supplied with the names and addresses of all participating site Principal Investigators (PIs). Trial staff at NCTU will perform this task.

On receipt of the signed investigator statement, approved delegation of responsibilities log and staff contact details, written confirmation will be sent to the site PI. The trial manager or delegate will notify the PI in writing of the plans for site initiation. Sites will not be permitted to recruit any patients until a letter for activation has been issued. The Trial Manager or delegate will be responsible for issuing this after a green light to recruit process has been completed.

The site must conduct the trial in compliance with the protocol as agreed by the Sponsor, Health Research Authority (HRA) and, by the regulatory authority (as appropriate), and which was given favourable opinion by the Research Ethics Committee (REC). The PI or delegate must document and explain any deviation from the approved protocol and communicate this to the trial team at NCTU.

A list of activated sites may be obtained from the Trial Manager.

6.3 Participants

6.3.1 Eligibility Criteria

6.3.1.1 Participant selection

There will be **NO EXCEPTIONS** (waivers) to eligibility requirements at the time of randomisation. Questions about eligibility criteria should be addressed PRIOR to attempting to randomise the participant.

The eligibility criteria for this trial have been carefully considered and are the standards used to ensure that only medically appropriate participants are entered. Participants not meeting the criteria should not be entered into the trial for their safety and to ensure that the trial results can be appropriately used to make future treatment decisions for other people with similar diseases or conditions. It is therefore vital that exceptions are not made to these eligibility criteria.

Participants will be considered eligible for enrolment in this trial if they fulfil all the inclusion criteria and none of the exclusion criteria as defined below.

In the event a patient fails screening due to presentation with self-reported respiratory tract infection within four weeks of screening or change in asthma medication within six, they may be re-screened once four weeks have elapsed since respiratory tract infection symptom onset or six weeks after change in medication. Patients may be re-screened for any reason if deemed appropriate by the principal investigator.

6.3.1.2 Participant Inclusion Criteria

- 1. aged \geq 18 years. N-ERD does not occur at birth and it rarely occurs in children.
- 2. diagnosis of N-ERD according to one of the following:
 - i. Positive aspirin challenge plus a history of nasal polyposis or asthma.
 - ii. More than one typical reaction to NSAIDs or aspirin plus a history of nasal polyposis or asthma.
 - iii. A single typical reaction to NSAIDs or aspirin and a history of nasal polyposis plus moderate to severe asthma.*

- iv. History of nasal polyposis plus asthma plus blood eosinophilia (≥300x10⁶/L) or raised FeNO (>25ppb) within last 12 months plus urinary leukotriene E4/creatinine >800pg/mg.
- 3. ACQ mean score of more than 1.5 as this indicates poor control. This is required to ensure there is a clinical need or a requirement to alter medication.
- 4. stable disease, as evidenced by a lack of change in asthma therapy within the last 6 weeks.
- 5. Adequate understanding of English (or Welsh) as participants will be required to complete questionnaires as part of the study.

* Defined as asthma at least "additional-add on therapy" as defined by the BTS/SIGN158 British guidelines on the management of asthma (https://www.brit-thoracic.org.uk/quality-improvement/guidelines/asthma).

6.3.1.3 Participant Exclusion Criteria

- 1. Tolerant to aspirin or NSAID with no respiratory or nasal reaction on exposure.
- 2. Significant cardiac disease, respiratory disease or other cause for breathlessness which, according to the principal investigator, contributes to the patient's symptoms of breathlessness or other respiratory symptoms to a greater degree than the patient's asthma.
- 3. Severe or uncontrolled co-morbid disease (other than nasal polyps) which is likely to affect the outcome of the study.
- 4. Having had an upper or lower respiratory tract infection requiring antibiotics within four weeks of randomisation.
- 5. Receiving biologic agents.
- 6. Receiving n-3 fatty acid oral supplements or more than two dietary portions of oily fish per week.
- 7. Current smoker or more than 15 pack-year smoking history.
- 8. Consumption of more than 21 units of alcohol per week as alcohol-induced respiratory symptoms are more common in N-ERD.
- 9. Pregnant or breastfeeding women and those less than 4 weeks postpartum.
- 10. Women of Child Bearing Potential (WOCBP) not using a highly effective form of contraceptive for the duration of participation in the study. A woman is considered of childbearing potential (WOCBP), i.e. fertile, following menarche and until becoming post-menopausal unless permanently sterile. Permanent sterilisation methods include hysterectomy, bilateral salpingectomy and bilateral oophorectomy at least 6 weeks prior to enrolment. Pregnancy tests will be required at trial start and at 12 weeks. Highly effective forms of contraception defined as: Methods of birth control which result in a low failure rate (i.e. less than 1% per year) when used consistently and correctly such, as implants, injectables, combined oral contraceptives, some intrauterine devices (IUDs), sexual abstinence (defined as refraining from heterosexual intercourse during the entire period of risk associated with the study treatments) or vasectomized partner. This will apply to all women under 55 years of age unless they are postmenopausal or sterile. Postmenopausal is defined as no menses for 12 months without an alternative medical cause. A high follicle stimulating hormone (FSH) level in the postmenopausal range may be used to confirm a post-menopausal state in women not using hormonal contraception or hormonal replacement therapy. However in the absence of 12 months of amenorrhea, a single FSH measurement is insufficient.
- 11. Participation in the active phase of another CTIMP or within 4 weeks (or the half-life of the drug if longer) of last study drug administration. Participation in observatory trials can occur if agreed between the PI of each trial and where this does not impact the patient or the outcomes of either trial.
- 12. Patients unable to give written informed consent.
- 13. Hypersensitivity to the active substance, soya, peanut, or any of the excipients.

Patients will be recruited into the study independent of gender, sexual orientation, marital status, disability, ethnicity, religion or belief. Pregnant women cannot be entered into the study as pregnancy itself may influence the ACQ and therefore the results of the study; however, women >4weeks postpartum can be randomised if they meet the remaining entry criteria. The research will be conducted within secondary care research sites.

Investigators are encouraged to contact the PUFFIN CI, via the NCTU trial team, for guidance in assessing eligibility in relation to exclusion criteria prior to approaching the patient about the trial if required.

6.3.1.4 Co-enrolment Guidance

Concurrent participation in clinical trials of investigational medical products is not permitted. Concurrent participation is defined as within 4 weeks of the last study drug administration (or at least one half-life if longer than 4 weeks). However, participants may be entered into other observational studies given prior agreement from the CI of both studies.

6.3.1.5 Screening Procedures and Pre-randomisation Investigations

Written informed consent to enter and be randomised into the trial must be obtained from participants after explanation of the aims, methods, benefits and potential hazards of the trial and **BEFORE** any trial-specific procedures. The only procedures that may be performed in advance of written informed consent being obtained are those that would be performed on all patients in the same situation as part of usual standard of care.

6.4 Interventions

6.4.1 Active treatment arm

6.4.1.1 Products

Eicosapentaenoic acid (EPA) plus docosahexaenoic acid (DHA) in a 1.3:1 ratio; respectively, in a white opaque capsule

6.4.1.2 Treatment Schedule

Participants will be asked to take six grams (as 6 x 1g capsules) once daily or in divided doses, with food.

6.4.1.3 Dispensing

Participants will have investigational medicinal product (IMP) dispensed three-monthly. The IMP will be supplied in bottles containing 120 capsules. Where a participant attends a clinic for baseline visit and randomisation is able to take place, the site should aim to dispense the IMP on the same day so that it can be collected by the participant. If a baseline visit has been conducted remotely or due to other exceptional circumstances, the site will have the option to request a courier to send IMP to the participant, see section 6.4.3 below. A dosing card will be dispensed with the IMP stating the required treatment schedule.

6.4.1.4 Dose Modifications, Interruptions and Discontinuations

If a participant forgets to take a dose and it is more than 24 hours after their scheduled dose, they should omit the missed dose and take the next dose when it is due. Participants must not take a double dose to make up for a forgotten dose. Interruptions should be avoided where possible, any reported should be recorded on the eCRF. Participants unable to continue with the IMP due to adverse reaction

or intolerability may reduce to four grams (as 4 x 1g capsules) per day. They must discuss this decision with the site research team and the date of reduction needs to be recorded in the eCRF.

6.4.2 Placebo Arm

6.4.2.1 Products

Placebo 6g palm olein IV 56 in a white opaque capsule (manufactured to appear identical to IMP).

6.4.2.2 Treatment Schedule

Participants will be asked to take six capsules once daily or in divided doses, with food.

6.4.2.3 Dispensing

The PUFFIN trial is a double-blind study and so dispensing for the placebo arm will be managed identically to the active arm (see section 6.4.1.3).

6.4.2.4 Dose Modifications, Interruptions and Discontinuations

If a participant forgets to take a dose and it is more than 24 hours after their scheduled dose, they should omit the missed dose and take the next dose when it is due. Participants must not take a double dose to make up for a forgotten dose. Interruptions should be avoided where possible, any reported should be recorded on the eCRF. Participants unable to continue with the IMP due to adverse reaction or intolerability may reduce to 4 capsules per day. They must discuss this decision with the site research team and the date of reduction needs to be recorded in the eCRF.

6.4.3 Accountability

The UK manufacturer will be responsible for drug accountability of centrally held drug and placebo. Each site pharmacy will be responsible for drug accountability of drug and placebo received at their site, this includes records of drug and placebo received at the pharmacy, dispensed to participants and unused drug and will ensure batch recall is possible in event of it being necessary. The UK manufacturer are also responsible for ensuring centrally held IMP is handled and stored appropriately, and for shipping IMP to each site. Each site pharmacy will be responsible for ensuring IMP and placebo is dispensed accurately to each participant at an appropriate clinic visit or in exceptional circumstances, liaising with NCTU and receiving CI approval, and suitably packaging for couriering to the participant's home address during trial participation (upon receipt of an appropriately signed prescription).

Unused IMP and placebo held centrally will be destroyed by the UK manufacturer. Undispensed IMP and placebo at site pharmacies will be disposed of by the site pharmacy. Participants will be asked to bring unused IMP and packaging to the relevant study visit to assess adherence to trial medication. After final accountability/capsule counts have been undertaken these should be disposed of at site by the research nurse using a special medicine bin (blue lid) or via pharmacies, according to their usual processes and the destruction log updated. Where this is not possible participants will be encouraged to dispose of the capsules via community pharmacies.

6.4.4 Compliance and Adherence

Compliance to study treatment, in the form of returned capsule counts, will be monitored as part of drug accountability at relevant visits as outlined in section 6.6.

6.4.5 Concomitant Care Standard Care

Patients will be managed according to the BTS/SIGN158 British guideline on the management of asthma (https://www.brit-thoracic.org.uk/quality-improvement/guidelines/asthma). This includes the use of bronchodilators, inhaled corticosteroids and theophylline. Participants may receive leukotriene receptor antagonists but not biologics. Acute asthma attacks may be managed with oral corticosteroids and antibiotics as appropriate. Patients will be withdrawn from the study if they undergo nasal polypectomy.

Concomitant medication

Patients must be receiving stable treatment for asthma and nasal disease related to N-ERD for at least 4 weeks prior to randomisation and not have any planned amendments for at least 4 weeks post-randomisation.

All concomitant medication including over the counter and herbal remedies will be recorded at baseline with any changes during participation recorded.

Non-permitted medication

The following medications are not permitted due to interactions, described in the SPC, with n-3 PUFA as outlined below and thus patients are **excluded** from the study (see section 6.3.1.3):

None

Omega-3 ethyl ester 90 should be used with caution in patients with known sensitivity or allergy to fish.

Increased monitoring

Concomitant medication requiring increased monitoring:

• Warfarin – monitored for increase in international normalised ratio (INR) and prothrombin time.

Omega-3 ethyl ester 90 as Omacor has been given in conjunction with warfarin without haemorrhagic complications. However, the prothrombin time must be checked when Omega-3 ethyl ester 90 is combined with warfarin or when treatment with Omega-3 ethyl ester 90 is stopped.

Sites are responsible for providing increased monitoring for participants receiving the abovementioned medication(s) and for any others the PI or sub-investigator deem appropriate. Results of additional monitoring procedures do not need to be recorded on the eCRF.

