6.4.7 Protocol Treatment Discontinuation

In consenting to the trial, participants are consenting to trial treatment, trial follow-up and data collection. However, an individual participant may stop treatment early or be stopped early for any of the following reasons:

- Unacceptable treatment toxicity or adverse event.
- Inter-current illness that prevents further treatment.
- Any change in the participant's condition that in the clinician's opinion justifies the discontinuation of treatment.
- If a participant becomes pregnant, they will be advised to stop trial treatment immediately (and if 12 week dispensing was scheduled this will not take place). The participant can and should be encouraged to remain in the trial for follow up measures as far as possible.
- Withdrawal of consent for treatment by the participant.
- Where patients are unable or unwilling to continue to undertake study measurements/activities, the decision as to whether the participant should continue with trial treatment and/or follow-up assessments will be at the discretion of the local PI and/or CI.

As participation in the trial is entirely voluntary, the participant may choose to discontinue trial treatment at any time without penalty or loss of benefits to which they would otherwise be entitled. Although not obliged to give a reason for discontinuing their trial treatment, a reasonable effort should be made to establish this reason, whilst remaining fully respectful of the participant's rights.

Participants who discontinue protocol treatment, for any of the above reasons, should remain in the trial for the purpose of follow up and data analysis.

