6.6.3 Early Stopping of Follow-up

Sites must inform NCTU of all forms of early trial discontinuation via the eCRF. In instances where a participant has decided to withdraw consent, it is essential for the site to establish which aspects of the trial the participant is withdrawing consent from.

- If a participant chooses to discontinue their trial treatment, they should continue to be followed up as closely as possible to the follow-up schedule defined in the protocol, providing they are willing. They should be encouraged and facilitated not to leave the whole trial, even though they no longer take the trial treatment.
- If, however, the participant exercises the view that they no longer wish to provide data either through study visits or remotely via the registry, this view must be respected, and the participant withdrawn entirely from the trial. Data already collected will be kept and included in analyses according to the intention-to-treat principle for all participants who stop follow up early. Any samples provided by the participants, which have yet to be analysed will be destroyed and the registry will be updated so that no further data is provided to NCTU.

Where patients are unable or unwilling to continue to undertake study measurements/activities, the decision as to whether the participant should continue with trial treatment and/or follow-up assessments will be at the discretion of the local PI and/or CI.

Participants who stop trial follow-up early will not be replaced.

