7.1 Research Ethics and Health Research Authority Approval

Before initiation of the trial at any clinical site, the protocol, all informed consent forms and any material to be given to the prospective participant will be submitted to the relevant REC and to HRA for approval. Any subsequent amendments to these documents will be submitted for further approval.

The rights of the participant to refuse to participate in the trial without giving a reason must be respected. After the participant has entered the trial, the clinician remains free to give alternative treatment to that specified in the protocol, at any stage, if s/he feels it to be in the best interest of the participant. The reasons for doing so must be recorded. After randomisation the participant must remain within the trial for the purpose of follow up and data analysis according to the treatment

option to which they have been allocated. However, the participant remains free to change their mind at any time about the protocol treatment and follow-up without giving a reason and without prejudicing their further treatment.

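### Section 6.4.5 withdraws participants from the study after nasal polypectomy, at odds with 7.1; followed as written, it creates avoidable missing outcome data

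*Protocol*

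**What the plan says.** Section 6.4.5, on concomitant care, gives an unqualified rule: "Patients will be withdrawn from the study if they undergo nasal polypectomy". The rule concerns the study, not only the capsules.

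Section 7.1 lets the treating clinician depart from protocol treatment: "the clinician remains free to give alternative treatment to that specified in the protocol, at any stage". It then states: "After randomisation the participant must remain within the trial for the purpose of follow up and data analysis". The only exception it gives is the participant's own freedom to change their mind.

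Three other sections show the general policy:

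- 6.4.7 lists reasons for stopping trial treatment, among them "Any change in the participant's condition that in the clinician's opinion justifies the discontinuation of treatment", and concludes: "Participants who discontinue protocol treatment, for any of the above reasons, should remain in the trial for the purpose of follow up and data analysis". Polypectomy is not on the list.
- 6.6.3 says of those who stop treatment: "They should be encouraged and facilitated not to leave the whole trial, even though they no longer take the trial treatment". It gives the local PI and/or CI discretion only in a stated situation: "Where patients are unable or unwilling to continue to undertake study measurements/activities, the decision as to whether the participant should continue with trial treatment" is left to them, and the same goes for further assessments. It adds: "Participants who stop trial follow-up early will not be replaced".
- 6.11.3 has a participant who becomes pregnant stop the capsules but encourages her to stay in follow-up.

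Section 6.10.4.4 defines the intention-to-treat population as everyone randomised, whatever their adherence.

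**The concern.** Stopping treatment and leaving follow-up are separate matters in this protocol (6.4.7 and 6.6.3). Section 6.4.5 uses the language of leaving the study, for an event decided by a clinician rather than by the participant. A site that follows it would stop assessing someone who is willing to continue; a site that follows 7.1 would carry on. Sites could therefore act differently on the same event.

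The event is not remote from the disease. Two of the four diagnostic routes in 6.3.1.2 require a history of nasal polyposis and the other two accept it, and exclusion 3 in 6.3.1.3 expressly spares nasal polyps from the bar on uncontrolled co-morbidity. Need for surgery may reflect nasal disease after randomisation and, if the treatment affects the nose, could depend on arm. Ending observation at that point risks informative missingness, most directly for SNOT-22 and PNIF and indirectly for the primary ACQ-6. Because the rule governs what is collected, a statistical analysis plan cannot repair it afterwards.

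**Working it through.** **1. Is there a conflict?** Take a willing participant whose clinician arranges polypectomy at week 10.

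| Section | Instruction |
|---|---|
| 6.4.5 | Withdraw from the study |
| 7.1 | Alternative treatment allowed; participant stays for follow-up and analysis |
| 6.4.7 | Does not name polypectomy; those stopping capsules for a listed reason stay |
| 6.6.3 | Encourages staying; PI/CI discretion only if unable or unwilling to continue measurements |

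Only 6.4.5 and 7.1 give opposite instructions. The other two show that 6.4.5 is out of line with policy, not that they contradict it.

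**2. What is lost and what is kept?** After surgery, the remaining ACQ-6, SNOT-22, PNIF and other scheduled assessments would stop. Data already collected are kept (6.6.3). ACQ-6 is also scheduled at weeks 6, 12 and 18, and the final visit has a window of 4 weeks either side, so it can take place from week 20 (6.6, 6.6.1.9). Vital status and hospital admissions are still sought (6.6.5).

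**3. Sample size.** Inputs from 6.7: SD 0.67, difference 0.5, 90% power, significance level 0.05 (two-sided assumed; the protocol does not say), 20% withdrawal. A two-sample t-test needs 38.7, so 39 per arm. 39 / 0.8 = 48.75, so 49 per arm and 98 in total, which matches the protocol.

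- 39 per arm evaluable: power 0.902.
- 38 per arm, one further loss in each arm: power 0.894.

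Polypectomy withdrawals that fit within the 20% allowance therefore leave planned power where it was.

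**4. Illustration of bias.** The protocol gives no polypectomy rate. Let k be the number lost in an arm of 49 and d the unseen mean minus the seen mean, with any other losses assumed to resemble those seen. Then

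true arm mean = seen arm mean + (k / 49) × d.

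For k = 1 and an assumed d of 0.5 to 1.0:

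- 0.5 / 49 = 0.0102, and 0.0102 / 0.5 = 2.0% of the target difference.
- 1.0 / 49 = 0.0204, and 0.0204 / 0.5 = 4.1% of the target difference.

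If imputation from earlier ACQ-6 values recovered half the gap (assumed), these become 0.0051 and 0.0102.

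The error in the complete-case difference (active minus placebo) is (k_placebo × d_placebo − k_active × d_active) / 49. Because d may differ between arms, the imbalance in numbers does not determine the error: equal losses need not cancel. The sign of d is also open, since unseen values may be worse because the disease progressed or better because of the operation.

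**The case against.** A specific rule is normally read as an exception to a general one, and 7.1 is a general ethics paragraph. On that reading there is no contradiction, only a design choice, and one with a rationale: polypectomy acts directly on the nose, so later SNOT-22 and PNIF mix surgery with capsules. If surgery were commoner on placebo, keeping those values could dilute a real nasal effect. The protocol also limits the damage. Treatment for nasal disease must be stable before entry with no planned change for at least 4 weeks after randomisation (6.4.5), two diagnostic routes do not require polyps, only values after surgery are lost, and 6.10.4.5 foresees multiple imputation and, if needed, worst-case or pattern-mixture analyses.

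Much of this stands as mitigation, and the confounding of nasal scores is real. It does not rescue the rule. The protocol states no order of precedence, and if 6.4.5 does prevail, the avoidable loss is confirmed. Concern about nasal scores is no reason to stop ACQ-6 as well. Possible influence on outcomes is not treated elsewhere as grounds for removal: pregnancy is said to affect the ACQ (text after 6.3.1.3), yet 6.11.3 favours follow-up, and 6.4.5 itself allows oral corticosteroids for asthma attacks without withdrawal. Values that are collected can be set aside in an analysis; values never collected can only be modelled.

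A reader might infer that these participants drop out of the intention-to-treat analysis altogether. The documents do not support that: 6.6.3 keeps their earlier data under the intention-to-treat principle.

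**Conclusion.** The point holds as an unreconciled inconsistency between 6.4.5 and 7.1 and as an avoidable source of possibly informative missing data. Minor to moderate.

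Two stronger readings are not supported. One is that the trial result will be materially biased, or biased in a known direction. With no polypectomy rate, size and sign are unknown and may be zero; about 0.01 to 0.02 per lost participant is an illustration under an assumed gap of 0.5 to 1.0, not a bound. The other is that the trial becomes underpowered, which does not follow while total losses stay within 20%. A link between surgery and arm is plausible from the trial's hypotheses about the nose, but nothing in the protocol establishes it.

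**What to change.** Replace the sentence in 6.4.5 with: *Participants who undergo nasal polypectomy remain in the trial, and all outcome assessments continue to week 24 if they are willing; whether trial capsules continue is decided by the clinician under 6.4.7.* Record the date of surgery in the eCRF as an intercurrent event and keep these participants in the intention-to-treat analysis.

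The cost is one sentence, through the usual amendment process, and one eCRF date. Sites already ask about changes in medical history at weeks 12 and 24 (6.6.1.7, 6.6.1.9). Questionnaires can be completed at home (6.6.1.1) and PNIF is captured at home where possible (6.5.2), so ACQ-6, SNOT-22 and PNIF need no extra clinic visit. The downside is that SNOT-22 and PNIF after surgery partly reflect the operation; a supplementary analysis of those two outcomes, set out in the SAP, can address it.
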